12.2.22. Prescription Drug Monitoring data

Number of opioid prescriptions found in the prescription drug monitoring database since last visit	#
--	---

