3.4. Duration

3.4.1. CM Group Course and Session Duration

Participants assigned to the CM arm will have contact with study staff at their first physician visit (intake visit at the Center for Addiction Science) and then at the following 4 physician visits that are scheduled as a regular buprenorphine-naloxone treatment course. These visits are often scheduled at 1 week, 2 weeks, 4 weeks, and 8 weeks following intake (see Figure 1). However, this varies with some patients, thus participation could potentially last 4 months as a result of them being seen on a monthly basis. Participation at each intervention session is expected to last for 10minutes for the assessment and 2 minutes for the intervention (“number wheel” gift card picker).

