3.6.2. Sessions 1-4: Intervention Treatment

- 1) Assessment questionnaires with interventionist
 - a) Assessment questionnaires completed (10 minutes)
- 2) Engage in either CM (2 minutes) or BSM (30 minutes)
 - a) BSM:
 - i) All BSM sessions will be audio-recorded in order for the study staff to evaluate treatment fidelity. Participants will be informed when the recording device is on, and permission to record will be obtained as soon as the recording device is started. Participants may refuse to have the session recorded and still participate. Audio recordings will be de-identified and labeled with a Study ID number stored on an encrypted computer.
 - b) CM:
 - i) A number wheel (pickerwheel.com) with varying levels of gift cards (ranging from \$25 to \$100) will be available.
 - ii) Urine toxicology will be obtained from the chart to assess presence of buprenorphine in urine (criteria for reward).
 - iii) Participants will be informed of the buprenorphine toxicology result.
 - (1) **IMPORTANT: IT IS BUPRENORPHINE IN URINE THAT RESULTS IN A GIFT CARD WIN.**
 - (2) **We ARE NOT providing feedback to the participant about the use of illicit substance presence in urine as this is not criteria for reward.**
- 3) Chart Review Following Intervention

- a) Information about buprenorphine-naloxone dose, all urine screen results (13 panel), and other substance use disorder diagnosis will be copied from the participant's medical chart.
- b) Opioid prescriptions will be obtained from prescription drug monitoring database.

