12.2.20. Dosage of Buprenorphine-Naloxone Prescribed

(obtained from medical record at each session .)	
Medication name	
Mg prescribed (buprenorphine)	
MME calculation	

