Statistical Analysis Plan: SMART Project 3 (Efficacy Study)

Because these analyses will focus on determining and intervention feasibility and satisfaction, and preliminary intervention effect sizes (with less concern focused on testing for statistical significance), outcome analyses will be conducted using a separate analysis for each outcome at each follow up observation. To compare groups, baseline and follow up variables will be entered into a 5 (baseline vs. follow ups at 1, 2, 3, and 4 weeks) by 2 (CM vs. BSM) analysis of variance (ANOVA) which will yield effect sizes for time, and interactions of time by intervention. The primary dependent variables will be attendance at physician visits, saliva drug screen data (positive for buprenorphine and negative for illicit opioids), and prescription drug monitoring. We hypothesize that a greater number of CM participants will demonstrate adherence to buprenorphine-naloxone than BSM, but that those randomized to BSM will report increased time allocated to substance-free activities, decreased delayed reward discounting, and demand for opioid.

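### The prescription-monitoring outcome is a raw count over unequal look-backs with no baseline window, so its time effect can come from visit spacing alone

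*Protocol*

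**What the plan says.** - **The variable.** Protocol section 12.2.22 defines it as the "Number of opioid prescriptions found in the prescription drug monitoring database since last visit". Section 3.6.2 adds only the source: "Opioid prescriptions will be obtained from prescription drug monitoring database". Neither gives a fixed window, a denominator in days or a rule on which drugs count.
- **When it is collected.** Table 1 (section 12.1) marks it at baseline, at the week 1, 2, 4 and 8 sessions, and at the 30-day chart review.
- **Visit spacing.** Section 3.4.1, and section 3.4.2 for the other arm: "These visits are often scheduled at 1 week, 2 weeks, 4 weeks, and 8 weeks following intake". Both say that spacing varies and that some patients are seen monthly.
- **Role in the analysis.** The SAP's list of primary dependent variables ends with screen results "positive for buprenorphine and negative for illicit opioids), and prescription drug monitoring". Its model is described thus: "baseline and follow up variables will be entered into a 5 (baseline vs. follow ups at 1, 2, 3, and 4 weeks) by 2" arms, "which will yield effect sizes for time, and interactions of time by intervention".
- **Related forms.** The dose log (section 12.2.19) asks for days since the last clinic visit, but Table 1 marks it at sessions only, not at baseline. The buprenorphine dose form (section 12.2.20) has a field for "MME calculation".

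**The concern.** A count over 28 days and a count over 7 days are not the same measurement. Entered side by side in a repeated-measures ANOVA, they make the time factor carry the length of the interval as well as any change in prescribing. At intake there is no previous study visit, so each abstractor has to choose a baseline window, and every comparison with baseline depends on that choice.

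The SAP puts effect sizes ahead of significance tests. What is at stake is therefore the size of the reported time effect, which could be carried into planning the next trial as if it showed a change in opioid prescribing.

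The term last visit is also open. It could mean the last clinic visit or the last study session, and these separate once a participant leaves clinic treatment but continues assessments, as sections 8.6 and 8.10 allow.

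**Working it through.** The documents give no rate, power or variance for this variable, so there is no figure to reproduce.

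**Step 1. Look-backs.** Differences between scheduled visits:
- Protocol, weeks 1, 2, 4, 8: 7; 14 − 7 = 7; 28 − 14 = 14; 56 − 28 = 28 days.
- SAP, weeks 1, 2, 3, 4: 7, 7, 7, 7 days.
- Baseline: undefined. A 30-day window is assumed below for illustration.

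**Step 2. Expected counts.** Expected count = rate per 28 days × look-back ÷ 28. At an assumed 0.5 per 28 days on the protocol schedule this gives 0.125, 0.125, 0.25, 0.5, a ratio of 1:1:2:4. The ratio does not depend on the rate.

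**Step 3. Effect on the ANOVA.** Assumptions: 20 per arm (section 3.5); independent Poisson counts; a rate constant over time and equal in both arms; mixed time-by-arm ANOVA at alpha 0.05 without sphericity correction; 2,000 replicates per setting. The Monte Carlo standard error is at most √(0.25/2000) = 1.1 percentage points. The entries are the percentage of simulated trials with a significant time effect when nothing changes.

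| Look-backs (days) | 0.1 per 28 d | 0.25 | 0.5 | 1.0 | Mean partial eta² |
|---|---|---|---|---|---|
| 7, 7, 14, 28 (protocol follow-ups) | 24 | 57 | 87 | >99 | 0.048 to 0.223 |
| 30, then 7, 7, 14, 28 | 30 | 74 | 98 | 100 | 0.050 to 0.229 |
| 7, 7, 7, 7 (SAP follow-ups) | 4 | 4 | 4 | 5 | 0.025 to 0.026 |
| 30, then 7, 7, 7, 7 | 33 | 74 | 97 | 100 | 0.053 to 0.263 |
| 7 at all five time points | 3 | 4 | 4 | 5 | 0.025 to 0.026 |

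The last column shows the range across the four rates. Unequal look-backs inflate the effect size itself, not only the p-value.

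**Step 4. Time by arm.** With the same schedule and rate in both arms, the unequal look-backs gave a significant interaction in 5% to 7% of trials, close to nominal. There are two routes to distortion:
- *Rates differ by arm but are constant over time.* With 1.0 versus 0.5 per 28 days, the expected difference on the protocol follow-ups is 0.125, 0.125, 0.25, 0.5. It grows although neither arm changes. The interaction was significant in 24% of trials, against 5% with equal look-backs.
- *Attendance differs by arm.* If last visit means clinic visit and visit 3 is missed, the week-8 look-back is 56 − 14 = 42 days, not 28. A participant who leaves the clinic after week 1 but continues assessments would have look-backs of 28 − 7 = 21 days at week 4 and 56 − 7 = 49 days at week 8. These overlap, so one prescription can be counted twice.

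**Step 5. Buprenorphine.** Assume one buprenorphine prescription per attended visit, that it appears in the database, and that it is counted. A participant adherent at all four visits then records 1, 1, 1, 1, a total of 4. One who leaves after visit 1 records 1, plus 0 to 2 other opioid prescriptions over eight weeks at 0 to 1.0 per 28 days, a total of 1 to 3. Counts tied to visits do not follow 1:1:2:4. Divided by days they would fall: 1/7, 1/7, 1/14, 1/28. The two kinds of prescription therefore cannot share one count, whichever analysis is chosen.

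**The case against.** The strongest reply has five parts.

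- *The SAP's own follow-ups are weekly.* This stands. On weeks 1 to 4 the follow-up look-backs are equal and the 1:1:2:4 pattern disappears. The undefined baseline does not.
- *The randomised comparison is protected.* This largely stands when both arms share schedule and rate. The SAP also mentions separate analyses at each follow-up, where look-backs are nominally the same in both arms. But the SAP asks for time effects too, and it hypothesises better adherence under CM. Since attendance is part of adherence, look-backs would differ by arm if that hypothesis is true and last visit means clinic visit.
- *Significance matters little in a pilot.* True, but the effect size is distorted as well.
- *Protocol section 3.3 does not list prescription monitoring among its primary outcomes.* This lowers the consequence. The SAP does list it, and demoting it would not repair the count.
- *The dose log already records days since the last clinic visit.* This makes the repair cheaper, but the field is not linked to the prescription item and is not collected at baseline.

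A reader might go further and infer that every opioid prescription, buprenorphine included, is counted, so that adherent participants look worse. The documents do not support that. They are silent on whether buprenorphine counts. Section 3.6.2 takes buprenorphine dose from the chart and opioid prescriptions from the database as separate items, and the MME field sits on the dose form. No scoring direction is given, and the SAP lists the variable beside two adherence measures. If buprenorphine prescriptions were read as adherence, a higher count would be favourable. The SAP also plans no total over visits.

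**Conclusion.** The unequal look-back is wrong as written. Following section 12.2.22 on the protocol's usual schedule gives a fourfold rise in expected count from the first to the fourth session with no change in prescribing. This needs no assumption beyond a constant rate and the stated visit weeks. How often it would yield a significant time effect (24% to over 99% on the four follow-ups) depends on the assumed rate and on Poisson counts.

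On the SAP's schedule the fault reduces to the missing baseline window; with an assumed 30 days the false time effect appears in 33% to 100% of trials. The two schedules contradict each other and must be reconciled. The fault lies mainly in the time effect, and it reaches time by arm only through differences between arms in attendance or prescribing rate.

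Whether buprenorphine is counted, and which direction is favourable, are points to clarify. They are not shown to be errors.

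**What to change.** 1. Reconcile the follow-up weeks in the SAP with those in the protocol.
2. Set one baseline look-back, for example the 30 days before intake.
3. State whether last visit means clinic visit or study session. Record the look-back start date, and have each interval begin where the previous query ended so that none overlap.
4. Analyse a rate: a count model with log days as offset, and arm, time and their interaction as terms. At the low assumed rate the whole trial would yield about 0.1 × 56/28 × 40 = 8 prescriptions over eight weeks, so the SAP should allow for a descriptive rate with an interval if the model is unstable. One fixed look-back at every time point is an alternative. On the protocol's schedule it should be no longer than 7 days, because a 30-day window at week 1 would reach 30 − 7 = 23 days before intake.
5. Abstract buprenorphine prescriptions and other opioid prescriptions in separate fields, and state the favourable direction of each.

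Cost: two or three form fields and a short SAP paragraph. Session intervals can largely be recovered from the dose log if clinic visit is meant. Where only totals were saved, the database must be queried again; no further contact with participants is needed.

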12.2.23. PEG for Chronic pain (3 items)

	0 No Pain	1	2	3	4	5	6	7	8	9	10 Pain as bad as you can imagine
What number best describes your pain on average in the past week?	0 No Pain	1	2	3	4	5	6	7	8	9	10 Pain as bad as you can imagine
What number best describes how, during the past week, pain has interfered with your enjoyment of life?	0 No Interference with Enjoyment	1	2	3	4	5	6	7	8	9	10 Completely Interfered with Enjoyment
What number best describes how, during the past week, pain has interfered with your general activity?	0 No Interference with Activity	1	2	3	4	5	6	7	8	9	10 Completely Interfered with Activity

12.2.24. EQ 5D 5L

Descriptive System items:					
Instructions: Select the answer that best applies to you	1	2	3	4	5
Answer score:					
MOBILITY	I have no problems in walking around	I have slight problems in walking around	I have moderate problems in walking around	I have severe problems in walking around	I am unable to walk around
SELF-CARE	I have no problems washing or dressing myself	I have slight problems washing or dressing myself	I have moderate problems washing or dressing myself	I have severe problems washing or dressing myself	I am unable to wash or dress myself
USUAL ACTIVITIES (e.g. work, study, housework, family or leisure activities)	I have no problems doing my usual activities	I have slight problems doing my usual activities	I have moderate problems doing my usual activities	I have severe problems doing my usual activities	I am unable to do my usual activities
PAIN / DISCOMFORT	I have no pain or discomfort	I have slight pain or discomfort	I have moderate pain or discomfort	I have severe pain or discomfort	I have extreme pain or discomfort
ANXIETY / DEPRESSION	I am not anxious or depressed	I am slightly anxious or depressed	I am moderately anxious or depressed	I am severely anxious or depressed	I am extremely anxious or depressed
VAS scale item					
Instructions:					
We would like to know how good or bad your health is today.					
This scale is numbered from 0 to 100.					
100 means the BEST health you can imagine.					
0 means the WORST health you can imagine.					
From 0 to 100, how good is your health today?					
Score (0 to 100):					

12.2.25. PHQ-2 depression 2 items

Instructions: Over the last 2 weeks, how often have you been bothered by the following problems?				
Score:	0	1	2	3
1. Little interest or pleasure in doing things	Not at all	Several days	More than half the days	Nearly every day
2. Feeling down, depressed or hopeless	Not at all	Several days	More than half the days	Nearly every day

12.2.26. GAD 2 anxiety 2 items only (also a 7 item version)

Instructions: Over the last 2 weeks, how often have you been bothered by the following problems?				
Score:	0	1	2	3
1. Feeling nervous, anxious or on edge	Not at all	Several days	More than half the days	Nearly every day
2. Not being able to stop or control worrying	Not at all	Several days	More than half the days	Nearly every day

12.2.27. Treatment history (times in treatment, medication used)

How many times have you been in treatment for opioid use disorder (addiction)?	(fill in number) If "0", end this questionnaire.		
Treatment #1 (most recent)			
How long were you in treatment (months)?	(fill in number of months)		
Was this counseling, medication, or both?	Counseling	Medication	Counseling and Medication
Was it successful (were you able to stop using opioids)?	Yes / No		
Treatment #2			
How long were you in treatment (months)?	(fill in number of months)		
Was this counseling, medication, or both?	Counseling	Medication	Counseling and Medication
Was it successful (were you able to stop using opioids)?	Yes / No		
Treatment #3... etc. up to 5 only			

12.2.28. Economy Contribution Questions

1.	Are you working? If yes	Yes	No
1.a.	How many hours a week?		
1.b.	How much do you make an hour?		
1.c.	How long have you been with your current employer?		
2.	Are you receiving SNAP/TANIF/SSDI/other public assistance?	Yes	No
3.	Have you had any police contact since last session ?	Yes	No

12.2.29. For Participants Who Have Stopped Center for Addiction Science Treatment Only

Are you receiving buprenorphine-naloxone treatment from a different provider at this time?	Yes / No
Are you receiving any treatment for opioid use disorder at this time?	Yes / No

12.2.30. Adverse Events

What was the adverse event? _____

Onset Date: ____ / ____ / ____

End Date: ____ / ____ / ____

Was the participant using the study drug(s) at the time of the event?

- Yes
- No

Was the event related to the study intervention or study drug?

- Unrelated
- Unlikely
- Possible
- Probable
- Highly Probable

Action Taken:

- None
- Study Drug Paused
- Study Drug Discontinued
- Study Participation Paused
- Study Participation Ended

If study participation was stopped, was it stopped due to the AE?

- Yes
- No
- N/A

Was the event expected?

- Yes
 No

Severity of AE:

- Mild
 Moderate
 Severe

SAE Category:

- Not an SAE
 Inpatient hospitalization
 AE resulted in death
 Life threatening
 Permanent or severe disability
 Congenital anomaly
 Treatment to prevent an above serious event

Outcome:

- Completely recovered
 Recovered with sequelae
 Condition improving
 Condition present and unchanged
 Condition deteriorated
 Death due to this AE
 Other
-
-
-

Narrative/Comments:

Staff Initials: _____

MD Check Off Initials _____

Date: ____ / ____ / ____

- Approved
 Needs QC

MD Additional Information Needed:

QC Completed By _____
QC Date: ____ / ____ / ____

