3.3. Design and Outcomes

This project will use a randomized design to compare treatment satisfaction and effectiveness of Contingency Management (CM) and Brief Motivational Intervention + Substance Free Activities Session + Mindfulness-Based Adherence Promotion (BSM) for medication adherence in patients who are initiating buprenorphine-naloxone treatment at our Center for Addiction Science (N=40). The interventions will take place across the first 4 physician visits of buprenorphine-naloxone treatment, starting after treatment intake.

Primary outcomes will include feasibility and satisfaction at the fourth weekly intervention visit, and an efficacy comparison of intervention group differences in buprenorphine-naloxone treatment adherence, defined as (1) attendance at physician visit AND (2) buprenorphine-naloxone presence in urine toxicology.

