4.3. Investigator and Staff Responsibilities

4.3.1. Investigators

[name] will be responsible for the day-to-day supervision of the project and all aspects of the planning, training, recruitment, assessment procedures, and evaluation of the interventions in the proposed study. In collaboration with the research team, [name] will be responsible for decisions about the development of the study protocol, the training needed for the research staff who will be conducting the intervention, and interpretation of the data analysis and manuscript and presentation preparation.

[name] will assist with recruitment from UTHSC Center for Addiction Science and provide the medical care associated with the buprenorphine-naloxone medication.

[name] [name] will serve as the study physician for reporting of Adverse Events associated with the intervention, not the buprenorphine-naloxone medication. Dr.

[name] will assist with decisions about the development of study protocol, interpretation of the data, and manuscript preparation.

[name] will oversee data cleaning, including qualitative data, and conduct all quantitative analyses. He will assist [name] with the rational assignment of participant clauses in qualitative analyses. He will prepare results for publication and assist in manuscript development.

[name] will participate in intervention development and interventionist training. He will also conduct treatment fidelity on an ongoing basis.

[name] will conduct economic analyses of the intervention costs based upon efficacy.

[name] will assist with the development of recruitment sites and advise on study design.

[name] will advise the development of the mindfulness aspect of the intervention.

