6. RECRUITMENT PLAN

Recruitment will occur through the CAS clinic and the American Recovery Clinic (ARC). [name] and the other physicians at the clinic will be informed of the eligibility criteria so they can note potential participants. At each patient's visit, the physician will tell the new patient they may be eligible to participate in research that will assist them in adhering to buprenorphine treatment. The physician will make sure to explain that this is not required and is different from what they are receiving as standard treatment. If the patient expresses interest, the doctor will bring the patient to a research room where a research staff member will explain the study. The staff member will check for eligibility, and if eligible, consent the participant. Additionally, staff members may approach the physician or clinic staff in regard to determining some eligibility criteria for the patients after reviewing the clinic's schedule of appointments.

Please see the "Alternative Procedures: COVID" section if in-person recruitment is not possible.

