8.11. Adverse Events

If patients experience an adverse event during the course of the study, we will conduct an assessment, complete an Adverse Event form, and follow the adverse event reporting system as required by our IRB and NIH regulations. We will assess Adverse Events at each intervention session.

Adverse events are defined as any untoward or unfavorable medical occurrence in a human subject, including any abnormal sign (for example, abnormal physical exam or laboratory finding), symptom, or disease, temporally associated with the subject's participation in the research, whether or not considered related to the subject's participation in the research.

Serious adverse events are any adverse event temporally associated with the subject's participation in research that meets any of the following criteria:

- (1) results in death;
- (2) is life-threatening (places the subject at immediate risk of death from the event as it occurred);
- (3) requires inpatient hospitalization or prolongation of existing hospitalization;
- (4) results in a persistent or significant disability/incapacity;
- (5) results in a congenital anomaly/birth defect; or
- (6) any other adverse event that, based upon appropriate medical judgment, may jeopardize the subject's health and may require medical or surgical intervention to prevent one of the other outcomes listed in this definition

At every session, we will assess both Adverse Events and Serious Adverse Events (AEs and SAEs).

All SAEs related to study participation are to be reported to the Project Manager who will report to the Study Physician (e.g., [name] [name]) within 24 hours of occurrence, and are to be reported to the UTHSC IRB immediately.

UTHSC's IRB operating procedures regarding AE's can be found here:

<https://www.uthsc.edu/research/compliance/irb/researchers/documents/adverse-event-reporting.pdf>

We do not anticipate any study related SAEs (we haven't observed treatment related SAEs in any of our studies) as our study involves an over-the-counter medication and psychosocial intervention.

A copy of the Adverse Events reporting tool is located in the Measures section.

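### The adverse-event form codes relatedness to the intervention and to an undefined study drug in one item, so the coded fields cannot separate the two

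*Protocol*

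**What the plan says.** The adverse-event form (Protocol section 12.2.30) asks "Was the event related to the study intervention or study drug" and gives one answer on five levels, from unrelated to highly probable. It also asks "Was the participant using the study drug(s) at the time of the event" with a yes/no answer. Two of its five action codes concern a study drug: one is "Study Drug Discontinued", the other is a pause.

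Elsewhere the manual describes a trial of two behavioral programs. Section 3.3 says that the randomized design is to "compare treatment satisfaction and effectiveness of Contingency Management (CM) and Brief Motivational Intervention" with its added components. In section 4.3.1 one investigator will "provide the medical care associated with the buprenorphine-naloxone medication", and the recruitment plan (section 6) has physicians tell patients that the research "is different from what they are receiving as standard treatment". Section 4.3.1 also names a study physician "for reporting of Adverse Events associated with the intervention, not the buprenorphine-naloxone medication".

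Section 8.11 defines adverse events without regard to cause, and then makes expedited reporting of serious events depend on cause: "All SAEs related to study participation are to be reported to the Project Manager". The same section says that the study involves an over-the-counter medication, which is described nowhere else in the documents.

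**The concern.** A relatedness code is useful only if the reader knows what the event was related to. Here one code serves two possible causes. One is what the trial tests; the other is treatment that participants receive from the clinic in any case. A positive code could be read as a harm of CM or BSM when the rater meant a medication effect, and a real intervention effect could be hidden among medication effects.

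The mixing need not be even between arms. CM rewards buprenorphine in urine, and the SAP hypothesizes that more CM than BSM participants will be adherent. If that happens, exposure to the medication, and with it the chance of a medication-related event, could be higher under CM. A merged code could not show whether an excess of related events came from the intervention itself or from more medication being taken. This is conditional; the documents give no event rates.

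The pilot also leads into Project 4, so a form carried forward unchanged would take the ambiguity with it.

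**Working it through.** The documents give no figure on this point to reproduce. The check sets the sections side by side and asks what the coded fields can show.

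**Inputs**
- Section 12.2.30: one five-level relatedness item naming two causes; one yes/no use item; two of five action codes about a study drug.
- Sections 3.3 and 3.5: CM and BSM are randomized, 20 participants each; no drug is assigned.
- Sections 4.3.1 and 6: buprenorphine-naloxone is clinic care, distinct from the research.
- Section 4.3.1: the study physician's reporting role separates intervention events from medication events.
- Section 8.11: adverse events are assessed at every session; expedited reporting of serious events refers to study participation; an over-the-counter medication is mentioned.

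**Step 1. Read study drug as clinic-prescribed buprenorphine-naloxone.** An answer of unrelated excludes both causes and is informative. An answer of possible or higher may mean the intervention, the medication or both. The use item helps only in part. A no argues against the medication, for example in someone who has left clinic treatment but is still assessed. A participant taking the medication as prescribed answers yes whatever caused the event.

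**Step 2. Read study drug as not applicable, since the trial assigns none.** The item then rates the intervention alone, and relatedness to the medication is not coded anywhere. The use item and the two action codes have no meaning.

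**Step 3. Read it as the over-the-counter product in section 8.11.** No such product appears in the design, the measures or the procedures, so this reading gives the rater nothing to rate.

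**Step 4. Compare.** No reading yields separate coded relatedness for the intervention and for buprenorphine-naloxone. The form does not record which reading the rater used, and the manual gives no completion rule.

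**Step 5. Scale.** Scheduled enquiries are at most 40 participants x 4 sessions = 160. This counts occasions on which the question is asked. It is neither a number of events nor an error rate.

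**The case against.** The strongest reply is that the form holds more than this one item. It has an event description, onset and end dates, a narrative, a physician check-off, a field for further information the physician needs, and a quality-control sign-off. A study physician who knows the remit in section 4.3.1 could sort events one at a time. This stands, and it limits the point to the coded fields. What remains is that no instruction asks anyone to record a separate attribution.

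A reader might infer more than the documents support in four ways:
- That the item feeds a safety comparison by arm for the DSMB. The SAP has no safety analysis. Section 9.2 says only that the board reviews the statistician's reports, and the charter is a separate document.
- That the item decides which serious events are reported. Section 8.11 does not say so, and its definition of an adverse event drops nothing on grounds of relatedness.
- That raters will code the same event in opposite ways. Nothing describes independent raters, so inconsistent coding is a possibility and has not been shown.
- That the manual states plainly that there is no study drug. The design supports that reading, but the over-the-counter statement in section 8.11 sits against it.

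It can also be said that this is leftover template text. That is plausible: the participant-withdrawal section mentions smoking cessation, and the satisfaction questionnaire (section 12.2.21, item 15) has answers about changing one's smoking. It remains an inference, and the form needs correcting whatever the origin.

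A last objection concerns the remedy. Both interventions aim to raise buprenorphine adherence, so a medication event could be an indirect result of the intervention. If only an intervention item counted as relatedness to study participation, the trigger in section 8.11 would become narrower. That objection stands and shapes the fix.

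**Conclusion.** The point holds for the coded data. One item merges two causes, one of the two is undefined, and section 4.3.1 relies on the distinction that is lost. It does not hold as a claim that the causes can never be told apart, because the free text and the physician's review may separate them in individual cases.

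Severity is minor. Sample size, error rates and the efficacy analysis are untouched, and the number of events affected is unknown. The conclusion rests on two assumptions: that the form is used as printed, and that no completion guide outside these documents tells raters how to read study drug. If such a guide exists, the gap shrinks to wording.

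**What to change.** Replace the single item with two, each on the existing five-level scale:
- (a) relatedness to CM, BSM or study procedures;
- (b) relatedness to buprenorphine-naloxone prescribed by the clinic.

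The two should not be mutually exclusive, so that an event thought to arise through both routes can be coded on both. Define study drug or replace the term wherever it appears on the form, including the use item and the two action codes.

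Reconcile the form with the physician's role in section 4.3.1 and with the over-the-counter statement in section 8.11. Leave the serious-event reporting trigger in section 8.11 as broad as it is now; the split is for attribution and should not be used to exclude events from reporting.

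The cost is one form and FileMaker edit, and a review of the narratives of events already recorded so that both items can be filled where the text allows. Where it does not, mark the attribution as undetermined.
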